8 STATISTICAL CONSIDERATIONS

8.1 Statistical design

8.1.1 Sample size

Design

A multi-center randomized placebo-controlled double-blind phase III trial investigating the effects of atorvastatin on breast cancer in the (neo)adjuvant setting.

Sample size

The sample size calculations are based on estimates of 10-year IDFS with an annual hazard rate of 0.0223. A sufficient number of patients is sought to provide 80% power using a two-sided 0.05-level test to detect a 25% reduction in the risk of an IDFS event (hazard ratio=0.75). A total of 379 events are required. With an estimated 5% drop-out at 5 years (annual rate 0.0103), this is estimated to be achieved by a total recruitment of 3,360 participants and a $6\frac{1}{2}$ years follow-up. The sample size estimate is based on inclusion for 3 years, a median follow-up of $6\frac{1}{2}$ year, that is 5 years of additional follow-up after the 3 years of inclusion.

Hypothesis

H0: (Neo)adjuvant atorvastatin treatment has no impact on invasive disease-free survival for breast cancer patients and survival rates do not differ between randomized groups; atorvastatin versus placebo.

Ha: Atorvastatin treatment influence invasive disease-free survival in breast cancer.

8.1.2 Randomization and stratification

Patients will be randomized electronically in a 1:1 manner through the DBCG CRF system. Access to randomize patients will require eligibility according to recorded in- and exclusion criteria. Randomization will be based on stratification for 1) trial site, 2) clinical setting (neoadjuvant/adjuvant early entry/adjuvant late entry).

8.2 Statistical analysis

Statistical and Analytical Plan

This is a phase III placebo-controlled adjuvant study to investigate the efficacy of atorvastatin in patients with operable early breast cancer. The protocol will accrue 3,360 patients all together randomized in a 1:1 ratio. The treatment phase will be two years followed by an observational phase of 6½ years follow-up for the initial data analysis. Patients will be followed in the clinic according to the current clinical guidelines in Denmark, and in addition patients will be asked to reply to questions regarding patient reported outcome in a RedCap-based questionnaire until year 10, please see Table 1. Follow-up for clinical events will be possible through clinical visits, medical records and the DBCG database, which will allow for detection of early as well as late recurrences, and long-term analysis executed as for 10-, 15- and 20-year survival rates. The data will be stored for 25 years after termination of the study.

A recurrence will be defined as any invasive breast cancer recurrence irrespective of localization. Information on overall survival will be retrieved by linkage to the national death registry.

Invasive disease-free survival among treatment groups will be analyzed in crude analysis using the Kaplan-Meier and Log-Rank test as well as the Cox regression hazards analysis with the latter allowing for confounder-controlled multivariable analysis.

Study Design

Significance level and power

The sample size calculations are based on estimates of 10-year IDFS with an annual hazard rate of 0.0223. A sufficient number of patients is sought to provide 80% power using a two-sided 0.05-level test to detect a 25% reduction in the risk of an IDFS event (hazard ratio=0.75). A total of 379 events are required. With an estimated 5% drop-out at 5 years (annual rate 0.0103), this can be achieved by a total recruitment of 3,360 participants and a $6\frac{1}{2}$ years follow-up. The sample size estimate is based on inclusion for 3 years, a median follow-up of $6\frac{1}{2}$ year, that is 5 years of additional follow-up after the 3 years of inclusion.

Accrual and Duration of Study

The study was initiated in January 2021. The estimated nation-wide accrual rate is 90 patients per month. Thus, patient accrual is expectedly completed within 4 years. Treatment duration time adds two years and the initial observational period adds another 5 years. In total, the time frame from study start to 5-year recurrence data is estimated to 10 years.

Given the bulk of patients with ongoing endocrine therapy who are eligible for the late entry stratum of the trial, this will be very pronounced within the beginning of the trial accrual.

All of the patients registered in the study will be accounted for besides patients already on a cholesterol-lowering drug who are enrolled in the observational cohort. The number of patients who were not evaluable, or who died or withdrew before treatment with STUDY MEDICATION began, will be specified. The distribution of follow-up time will be described, and the number of patients lost to follow-up will be provided.

Safety Monitoring

Adverse events will be recorded in the MASTER trial CRF in the DBCG database and monitored on an ongoing basis during active treatment and their frequencies reported to the sponsor equal to the coordinating national trial site, Department of Oncology, Aarhus University Hospital. Toxic effects will be categorized using a modified version of the NCI Common Terminology Criteria for Adverse Events, Version 5.0.

For reporting of adverse events, please see protocol chapter 14.

9 PHARMACOKINETICS

Atorvastatin is a well-documented drug and additional pharmacokinetics will not be performed within this trial.

10 TRANSLATIONAL RESEARCH

Translational research will be performed in co-operation with the laboratory units at the trial sites participating in this protocol.

Tumor samples will be treated and stored according to current research ethical practice in Denmark in a research biobank assigned for this trial. Blood samples of a total of 30 ml/time are drawn at three time points: at baseline and at 1 and 2 years after inclusion. And for patients in neo-adjuvant cohort also a

blood sample at 6 months. Frozen blood samples will be stored in a research biobank at the Danish Cancer Biobank. Potential left-over blood after the analyses for this study, are stored in the research biobank in the Danish Cancer Biobank for future, not yet specified, research.

Pathological samples are stored according to clinical routines at the Departments of Pathology affiliated with the trial sites although one tissue block is set aside for the MASTER study, and upon completion of trial enrollment, triplet sample cores of 1 mm in diameter are arranged in a tissue microarray (TMA) and stored in a research biobank at the DBCG biobank for future research (RH-2015-122, I-Suite nr: 03903). The biological samples will be used for analyses in relation to the following translational endpoints:

Tumor tissue sampled at baseline (for neoadjuvant patients both at diagnosis and at surgery)
will be analysed for biomarkers of prognosis and treatment prediction; i.e. HMGCR, LDL-R
expression along with HMGCR down-stream products in the mevalonate pathway (e.g.
farnesyl-pyrophosphatase, geranylgeranyl-pyrophosphatase and phosphorylated-ERK, the
latter indicating an activated Ras pathway).

Serum, plasma and whole-blood collected at baseline and during follow-up will be analyzed for prognostic and predictive markers, i.e. LDL, HDL, cholesterol, triglycerides, Apo-A, and Apo-B, HMGCR SNP's, circulating antibodies and circulating tumor-DNA (ctDNA), the latter to monitor the burden of circulating ctDNA according to treatment response as well as to investigate specific mutations for their potential treatment predictive value, i.e. TP53 mutations.

The data center for the translational parts of this trial is housed at the Department of Oncology, Aarhus University.

11 INVESTIGATOR AUTHORIZATION PROCEDURE

This is a multi-center trial and investigator authorization procedures are limited to the sponsor, the national PI and delegated investigators of this trial. The trial will be initiated following the approval of the regional ethical committee and medical products agency.

12 PATIENT REGISTRATION AND RANDOMIZATION

Patients eligible for the trial are offered inclusion into the study at the Departments of Oncology according to this schedule:

1) Neo. adjuvant behandling

Ved behandling	med EC-TAX
----------------	------------

Cohort:	Early Neo		Early ad	j.	Late adj.	Ingen inkl.
Behandling:	EC	TAX	Operation	Til og med mdr. 3	Mdr. 4 til og med år 3	År 4+5
_				Endokrin behandling		

Ved behandling med TAX-EC

Cohort:	Early Neo		Early ad	Late adj.	Ingen inkl.	
Behandling:	TAX	EC	Operation	Til og med mdr. 3	Mdr. 4 til og med år 3	År 4+5
_			·	Endokrin behandling		

2) Adjuvant behandling med kemoterapi

Ved behandling med EC-TAX

ved benandling med EC-TAX									
Cohort:		Early adj.	Late adj. Inger inkl.						
Behandling:	Operation	EC	TAX	Til og med mdr. 3	Mdr. 4 til og med år 3	År 4+5			
				Endokrin behandling					

Ved behandling med TAX-EC

Ved bending med TAX Le									
Cohort:		Early Late adj.							
Behandling:	Operation	TAX	EC	Til og med mdr. 3	Mdr. 4 til og med år 3	År 4+5			
_				Endokrin behandling					

Ved behandling med DC

ved bending fred be								
Cohort:		Early adj.		Ingen inkl.				
Behandling:	Operation	Første 3 serier DC	Sidste 3	Til og med mdr. 3	Mdr. 4 til og med år 3	År 4+5		
		sener DC	serier DC	Er	ndokrin behandling			

3) Adjuvant behandling uden kemoterapi

Cohort:		Early adj.	Late adj.	Ingen inkl.	
Behandling:	Onematica	Til og med mdr. 3	Mdr. 4 til og med år 3	År 4+5	
	Operation	Endokrin behandling			

The patient will receive oral and written information about the trial. Given a positive interest for participation in the trial, the patient will be offered time to consider participation prior to signing the informed consent. After signing, registration of in- and exclusion criteria in the DBCG database will be done, the randomization is performed, blood samples are taken, and STUDY MEDICATION provided to the patient along with practical information regarding RedCap access.

13 FORMS AND PROCEDURES FOR COLLECTING DATA

13.1 Case report forms and schedule for completion

All clinical data including adverse and clinical events are collected from clinical visits/medical records and arranged in the nation-wide DBCG CRF database according to Table 1. The DBCG CRF system is well-established in clinical routine for all breast cancer patients in Denmark, and collects data on imaging, pathology, surgery, and oncological treatment as well as follow-up data. In addition to the standard clinical data, which is also part of the trial data, there will be an added folder in the DBCG CRF for specific trial data not covered by the standard clinical data, i.e. adverse events and compliance regarding STUDY MEDICATION. Potential adverse events are evaluated at the clinical visits and reported into the DBCG CRF.

Patient reported outcomes (PRO) are sampled from RedCap-questionnaires (based on PRO-CTCAE, version 1.0, Danish) for which a separate link is sent out via email corresponding to each of the time points stated in Table 1, and patient replies are gathered in a RedCap database hosted at Aarhus University and subsequently copied into the DBCG database. The emails are sent automatically from the RedCap database system to the email address the patient has stated at the informed consent. Upon end of trial inclusion, data from patient reported outcome are copied into the DBCG database. Patients will be clearly informed that the PRO-data are collected for evaluation upon completion of study enrolment, which implies that the reported outcomes are not evaluated during the trial and thus, all potential AE´s are to be reported to their oncological doctor, who will decide on potential further actions.

Results from the translational blood tests and tumor biological data will subsequently be added into the MASTER trial database folder within the DBCG database.

The database will be stored at the data center at DBCG. Access to the full MASTER database will be limited to the national PI (sponsor), the steering committee, delegated investigators, trial nurses, and delegated monitors.

13.2 Data flow

Forms evaluating patient data including adverse events, blood samples, as well as pathological and translational parameters are handled by the PI, steering committee, delegated investigators, and site-specific trial nurses. In the case of missing or inconsistent data updating on data can only be required by the investigators, the steering committee, or trial nurses.

14 ADVERSE EVENTS

14.1 Definitions

An **Adverse Event (AE)** is defined as any untoward medical occurrence or experience in a patient or clinical investigation subject which occurs following the administration of the STUDY MEDICATION regardless of the dose or causal relationship. This can include any unfavorable and unintended signs (such as rash or enlarged liver), or symptoms (such as nausea or chest pain), an abnormal laboratory finding (including blood tests, x-rays or scans) or a disease temporarily associated with the use of the protocol treatment.

Common side effects (affects 1 to 10 users in 100) include:

- inflammation of the nasal passages, pain in the throat, nose bleed
- · allergic reactions
- increases in blood sugar levels
- increase in blood creatine kinase
- headache
- nausea, constipation, wind, indigestion, diarrhea
- joint pain, muscle pain and back pain
- blood test results that show your liver function can become abnormal

Side effects are registered in the MASTER folder in the DBCG CRF database.

An **Adverse Drug Reaction (ADR)** is defined as any response to a medical product, that is noxious and/or unexpected, related to any dose.

Response to a medicinal product (used in the above definition) means that a causal relationship between the medicinal product and the adverse event is at least a reasonable possibility, *i.e.* the relationship cannot be ruled out.

An **Unexpected Adverse Drug Reaction** is any adverse reaction for which the nature or severity is not consistent with the applicable product information (*e.g.*, Investigators' Brochure).

A **Serious Adverse Event (SAE)** is defined as any undesirable experience occurring to a patient, whether or not considered related to the protocol treatment. A Serious Adverse Event (SAE) which is considered related to the protocol treatment is defined as a **Serious Adverse Drug Reaction (SADR)**. The product resume for atorvastatin (TEVA) is the reference document used for evaluation of whether an SAE is expected or unexpected and thus may be classified as a Suspected Unexpected Serious Adverse Reaction (SUSAR).

Adverse events and adverse drug reactions which are considered as **serious** are those which result in:

- ♦ death
- a life-threatening event (i.e. the patient was at immediate risk of death at the time the reaction was observed)
- hospitalization or prolongation of hospitalization
- persistent or significant disability/incapacity
- events that lead to congenital malformation
- any other medically important condition (i.e. important adverse reactions that are not immediately life threatening or do not result in death or hospitalization but may jeopardize the patient or may require intervention to prevent one of the other outcomes listed above).

Events not to be reported as SAE

Due to the severity of the primary disease and the standard treatment hereof in patients participating in this trial, a number of events, where SAE reporting can be omitted, have been defined.

The following will not be considered for SAE in this study:

An event resulting in hospitalization or prolongation of hospitalization, if the only reason for hospitalization or prolongation are as follows:

Hospitalization secondary to breast surgery or expected chemotherapy toxicity such as:

- Fever
- Nausea and vomiting
- Neutropenia

Hospitalization secondary to expected cancer morbidity such as:

- DVT and pulmonary embolism
- Electrolyte disturbances
- Pain treatment
- Anxiety
- Reference to any (neo)adjuvant treatment and procedures
- Reference to chemotherapy
- Operation for IV access (ex. Port-a-cath)

The above events can be recorded in the adverse event CRF in the DBCG database.

Guidelines for connection between adverse events and treatment

The causal relationship between one of the test drugs and the adverse event judged by the investigator as either YES (related) or NO (not related). If there is a reasonable suspicion of a causal relationship to the study drug, i.e. that there is data (evidence) or arguments to suggest a causal link, the causal relationship between the drug and the incident is

assessed as YES. The criteria for evaluation of the correlation between drug and event will include consideration of potential interactions between medications in the regimen and the drugs, which the patient is also treated with.

The following criteria must be considered in the assessment of causality as YES:

- Reasonable temporal association with administration of the drug.
- It might be caused by the patient's clinical condition, environmental or toxic factors or other treatments that patients receive.
- Known response pattern of the suspected STUDY MEDICATION.
- Loss or decrease upon discontinuation of STUDY MEDICATION.
- Returns on resumption of STUDY MEDICATION.

The following criteria must be considered in the assessment of causality as NO:

- It does not follow a reasonable temporal sequence from administration of the drug.
- It can easily be caused by the patient's clinical condition, environmental or toxic factors or other treatments that patients receive.
- It does not follow a known pattern of response to the STUDY MEDICATION.
- It does not return or become worse when the STUDY MEDICATION is administered again.

14.2 Reporting procedure

Any SAE occurring from start of STUDY MEDICATION until 30 days after termination of STUDY MEDICATION should be reported to the sponsor center, Department of Oncology, Aarhus University Hospital, within 24 hours from the time the investigator became aware of the event (expedited reporting). A template for reporting serious adverse events (SAE) is provided all trial sites and upon an SAE, the filled SAE template is to be email to the sponsor site ([contact]). The SAE is implemented into the database and reported according to national regulations. Related SAEs MUST be recorded and reported, regardless of the time elapsed between the last study drug administration, even if the trial is completed. Non-related SAEs occurring during the trial until 28 days after the last dose of STUDY MEDICATION must be recorded and reported. Related SAEs are to be recorded and reported up to 24 months after completion of STUDY MEDICATION. Sponsor will report serious adverse and/or unexpected serious and suspected adverse reactions (SUSARs) as needed to investigators, the Medical Products Agency and the ethics committee in accordance with the relevant legal requirements and ICH's quidelines for Good Clinical Practice (GCP). Hereof, SUSARs, which are deadly or life threatening, are to be registered and reported to the Medical Product Agency as quickly as possible and at the latest 7 days after sponsor has been aware of such a presumed adverse event. All other SUSARs are to be reported to the Medical Product Agency later than 15 days after the sponsor has been notified.

Unblinding: In case an emergency in which unblinding of STUDY MEDICATION is deemed necessary, the procedure is as follows:

1. The patient, relatives or health personnel will find and can call the phone number stated at the trial specific card, which the participants receive upon inclusion, indicating the phone number to the Department of Oncology at their specific site, i.e. for Aarhus University Hospital:

Patienten deltager i et videnskabeligt forsøg:

KFE-XXXX - KALDENAVN Forsøgets titel: xxxxxxxxx

Forsøgsansvarlig læge: xxxlæge xxxxx xxxxx

Inden for 24 timer skal Klinisk Forsknings Enhed have besked om indlæggelsen på e-mail [contact].

Vagthavende på Kræftafdelingen: Tlf. [name]

2. Each site has staff at the hospital, who can unblind patients immediately, and each site must make a local, written procedure for unblinding.

Annual Safety Report: On a yearly basis during the trial, it is the responsibility of the sponsor to develop a list of all serious adverse events (SAEs), which have occurred during the trial period, together with a report of the trial participants safety.

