5.1.5 Duration of therapy

All patients will receive atorvastatin or placebo for two years with the exception mentioned in section 5.1.4 or in case of discontinuation requested by the patient. Atorvastatin is a well-documented drug prescribed for continuous use over several years and intercurrent illness would not indicate discontinuation of atorvastatin, unless symptoms are related to those mentioned in section 5.1.4.

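### Protocol section 14.2 ends the duty to report related SAEs both at 24 months and never, mismatches the non-related window by two days, and words the non-fatal SUSAR deadline backwards

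*Protocol*

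**What the plan says.** All the relevant sentences stand in the opening paragraph of Protocol section 14.2 (Reporting procedure).

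- Any SAE: "Any SAE occurring from start of STUDY MEDICATION until 30 days after termination of STUDY MEDICATION should be reported to the sponsor center". This sentence carries the 24-hour expedited duty.
- Related SAEs, first statement: "Related SAEs MUST be recorded and reported, regardless of the time elapsed between the last study drug administration, even if the trial is completed".
- For events judged unrelated: "Non-related SAEs occurring during the trial until 28 days after the last dose of STUDY MEDICATION must be recorded and reported".
- Related SAEs, second statement: "Related SAEs are to be recorded and reported up to 24 months after completion of STUDY MEDICATION".
- SUSARs that are fatal or life-threatening go to the agency "at the latest 7 days after sponsor has been aware of such a presumed adverse event".
- Remaining SUSARs: "All other SUSARs are to be reported to the Medical Product Agency later than 15 days after the sponsor has been notified".

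The same paragraph requires the sponsor to report in line with legal requirements and ICH good clinical practice, but it gives no order of precedence among its own sentences. No other section reconciles them.

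**The concern.** Sites work from this paragraph when they decide whether an event after the end of treatment has to be reported. For related SAEs it gives them two answers. The 24-month sentence comes later and is the more specific, so a site could reasonably take it as the operative limit. That site would then not report a related SAE arising after 24 months, although another sentence in the same paragraph makes the report mandatory. A different site, following the unlimited sentence, would report the same event. An SAE that was never reported cannot be recovered at the analysis stage.

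The two-day mismatch for non-related SAEs is the same kind of slip on a much smaller scale. The SUSAR sentence is a separate matter: as worded it sets an earliest time for reporting to the agency and no latest time.

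**Working it through.** The plan states no figure to reproduce here. The check sets the sentences side by side by SAE class and adds simple date arithmetic.

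**Related SAEs**

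| Sentence | End of the duty |
|---|---|
| First statement on related SAEs | none, continues after trial completion |
| Second statement on related SAEs | 24 months after completing study medication |

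Inputs: treatment lasts two years (section 5.1.5: "All patients will receive atorvastatin or placebo for two years"), and clinical events and survival are assessed yearly up to 10 years after inclusion (section 6.4). For a patient who completes treatment:

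- the 24-month limit falls at 2 + 2 = 4 years after inclusion;
- planned follow-up beyond it is 10 − 4 = 6 years.

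In that stretch, and after it, a related SAE must be reported under one sentence and lies outside the other. For a patient who stops early the limit falls sooner.

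**Non-related SAEs**

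| Sentence | End of the duty |
|---|---|
| Any SAE | 30 days after termination |
| Non-related SAEs | 28 days after the last dose |

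If termination and last dose are the same date, the gap is 30 − 28 = 2 days: an event on day 29 or 30 is inside one window and outside the other.

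**Across the two classes.** A shorter window for non-related than for related SAEs is an ordinary choice and no contradiction. There are therefore two conflicting pairs, one large and one trivial.

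**The 24-hour rule.** It is attached to the 30-day sentence. The paragraph does not say whether a related SAE found after day 30 must also reach the sponsor within 24 hours.

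**SUSARs.** The 7-day limit is phrased as a maximum. The 15-day limit that follows is phrased as a minimum. The context points to a dropped negation. The sentence governs when the sponsor informs the agency, so it does not alter which SAEs sites capture.

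**What lies outside the problem.** Section 7 makes patients evaluable for toxicity from baseline (T1) until treatment is discontinued (T5). The adverse event form in section 6.5 also stops at two years. Neither depends on the late window in section 14.2. Sample size, power and the definition of IDFS do not use it either.

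**The case against.** Every sentence is phrased as a duty to report, and none forbids later reporting. A site that reports all SAEs to day 30 and related SAEs without limit satisfies every sentence. That stands, and it rules out a stronger reading that a reader might infer, namely that the paragraph sets four mutually exclusive windows which cannot be obeyed together. The defect is narrower: the paragraph does not say where the duty ends, and it does not tell sites to take the longer limit.

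The 30-day sentence can be read as covering only expedited reporting, with the 28-day sentence covering routine recording. This is possible, though the former speaks of any SAE. Even if accepted, it leaves the 24-month and unlimited sentences opposed.

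Few events are likely to be affected. Section 14.1 lists a reasonable temporal association among the criteria for relatedness, and section 1.2 gives a plasma half-life of 7 hours, or 20 to 30 hours for the inhibitory activity. An event that first arises more than two years after the last dose will seldom be judged related. This stands as a limit on the size of the problem.

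A reader might also infer that the overall-safety endpoint has no defined window. The documents do not support that, because toxicity evaluation ends at T5 and section 6.4 provides for late effects through medical records and registry linkage, up to 20 years after diagnosis. Linkage does not, however, replace an investigator's judgement of relatedness or a report to the sponsor.

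Finally, the SUSAR sentence is evidently a drafting slip beside a requirement to follow the law, and it should not be read as an instruction to report late.

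**Conclusion.** The paragraph is wrong as written and should be corrected. The substantive conflict is the pair of end-points for related SAEs. On the assumption of a full two years of treatment, it covers about six of the ten planned follow-up years and anything later. That is a span of time and not a count of events: the protocol gives no rate of late related SAEs, and the number is probably small. Any share of follow-up time would depend on the horizon chosen and would not measure lost reports.

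The non-related mismatch amounts to two days and is minor. The SUSAR wording is a clear error in a regulatory instruction, with no effect on SAE capture. The primary endpoint, power and the on-treatment toxicity evaluation are untouched.

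**What to change.** Rewrite the paragraph so that each SAE class has one window, counted from one defined date. One way that loses no required report is to keep the longer limit already stated in each pair: all SAEs to 30 days after the end of study medication, and related SAEs without time limit. State whether the 24-hour rule applies to related SAEs found after day 30. Insert the missing negation in the SUSAR sentence so that 15 days is a maximum.

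The cost is one reworded paragraph and a note to sites. The downside is a few more late related SAEs to process. Sample size, randomization and endpoint definitions do not change.
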